9.1 Test drug

Non-proprietary name : sargramostim (Code name: NPC-26)

Dosage form/Strength : A lyophilized preparation containing 250 µg of sargramostim in 1 vial

Storage conditions : 4°C (2 to 8°C)

9.2 Packaging and labeling of test drug

The vials will be placed in individual packaging boxes. The label and package will contain the following information. Expiration date will be specified in a separate written procedure.

- A statement that the test drug is for clinical study use.
- Name and address of the sponsor.
- Identification number.
- Manufacturing number.
- Storage condition.

9.3 Physiological saline for dissolution of the test drug and for the control group

In the active treatment group in the study, the test drug will be dissolved in physiological saline and administered by inhalation. In the control group, the physiological saline itself will be administered by inhalation (see "10.3 Administration of study drug"). The physiological saline used in the study will not be supplied by the sponsor, but purchased by the medical institution.

Therefore, the records of storage, management, and delivery of physiological saline will not be applicable to "9.4 Management of test drug" in the next section.

9.4 Management of test drug

- (1) The sponsor will deliver the test drug and the " Investigational product handling procedures" to the Investigational product manager after a contractual agreement with the medical institution has been signed.
- (2) The Investigational product manager will store and manage the test drug in accordance with the " Investigational product handling procedures", and record the prescription at the medical institution, usage in each subject, disposition, and return of the test drug to the sponsor onto the Investigational product management sheet.
- (3) The Investigational product manager will store the used test drug, unused test drugs, and package, outer box at the appropriate time in accordance with the " Investigational product handling procedures " based on the rule of the medical institution until they are retrieved by the sponsor. Moreover, a copy of the Investigational product management sheet will be provided to the sponsor appropriately.

10 Study Procedures

This is a randomized, placebo-controlled, double-blind, group-comparison, multicenter study. Refer to Figure 6.1-1 for the study design.

10.1 Enrollment of subject

The investigators will assign a subject identification code to subjects in the order of giving informed consent, and enter the information of the eligible randomized subjects in the electronic case report form (eCRF). The subject identification code will be composed of a two-digit number assigned to each medical institution and a three-digit number assigned to each subject in ascending order from 001 within the medical institution connecting with a hyphen (ex. the subject identification code of the first subject in medical institution 01 is "01-001"). Moreover, a duplicable "Screening list" will be prepared. The following information will be included in the Screening list.

[First sheet]

Date of informed consent, subject's name, medical record number, subject identification code, date of screening test, and screening test results (by eligibility) will be recorded and stored at the medical institution.

[Second sheet]

Information other than the subject's name and the medical record number on the first sheet will be copied on the second sheet. After the clinical study has been terminated, the principal investigator will confirm the contents, sign and seal, or sign, and submit it to the sponsor.

The investigators will conduct observations/examinations on the day of allocation (Day 0) for eligible subjects based on the screening test results, ensure that the inclusion criteria are met, and enter the required information in the eCRF. This electronic entry will be regarded as enrollment of the subject, then the investigators will instruct the unblinded pharmacist to randomize the subject.

10.2 Randomization

Randomization will be performed by the unblinded pharmacist using the web-automated responsiveness system (IWRS) of the eCRF. The unblinded pharmacist shall be specifically in charge of allocation, preparation and arrangement of the study drug and must not perform any other study-related duties other than those assigned. The unblinded pharmacist must not disclose any information on allocation to others except the unblinded monitor. When the allocation code is recorded or duplicated for the purpose of preparation and arrangement of the study drug, the unblinded pharmacist shall strictly control these documents so that they are not seen by others. The unblinded pharmacist shall discard these documents in an appropriate manner as soon as possible after use.

Stratified allocation using standard treatment as the allocation factor will be performed at the randomization. Enrolled subjects will be randomized in a 2:1 ratio to either the active treatment group or the control group.

The investigators and the study collaborator other than the unblinded pharmacist should not be present at the operations for preparation and dispensing of the study drug performed by the unblinded pharmacist.

10.3 Administration of study drug

Administration of study drug will start in the morning of Day 1 (twice daily, in the morning and evening between Day 1 and Day 5).

In the active treatment group, 250 µg/vial of sargramostim will be dissolved in 4 mL of physiological saline, and 2 mL of which will be administered twice daily (in the morning and evening) using an inhaler for 5 days, in principle (up to 10 days). In the control group, 2 mL of physiological saline will be administered twice daily (in the morning and evening) using an inhaler for 5 days, in principle (up to 10 days).

Approximately 10-15 minutes will be taken for one inhalation administration which shall be continue until the prepared solution has been depleted. During the inhalation administration, air cleaner or similar will be available for prevention against infection for healthcare workers and other patients.

The start date and time of the study drug administration should be recorded in the eCRF. Details of the preparation and dispensing of the study drug should be in accordance with the procedures specified separately.

All subjects may continue to receive inhalation administration of the study drug at the discretion of the investigators for up to Day 10 from Day 6 onward. After Day 6, the dosage and administration should be the same as that in the first 5 days.

Occurrence of serious allergic or anaphylactic reactions after administration of sargramostim has been reported. If a serious allergic or anaphylactic reaction occurs, administration should be discontinued and appropriate therapy should be initiated. The investigators shall follow up at least 1 hour after inhalation administration to ensure that no clinical symptoms such as acute hypersensitivity reactions (e.g., facial or extremity swelling, cough, urticaria, decreased consciousness, respiratory distress) are observed.

10.4 Disclosure of allocation code in an emergency

When disclosure of allocation code in an emergency is requested by the investigators through the sponsor in the event of a serious adverse event, the unblinded pharmacist will disclose the allocation code of the subject in accordance with the procedures provided by the sponsor separately.

10.5 Unblinding after completion of clinical study

The allocation code for this study will be stored in the EDC system, but only the unblinded pharmacist and the unblinded monitors will be allowed to review the code during the study period. After completion of the clinical study, the data will be locked in the blinded condition according to the predetermined procedures, then the allocation code will be outputted from the EDC system and unblinded.

11 Concomitant Medication/Therapy

A standard treatment for each subject against COVID-19 will be chosen and performed appropriately based on medical judgment, with reference to current knowledge and guideline^{1, 16, 17}.

Concomitant use of any unapproved drugs (including off-label use of approved drug and use at unapproved dosage and administration, excluding steroids as standard treatment at each medical institution) will be prohibited throughout the study period (with an exception of concomitant medication/therapy given after study discontinuation when a subject meets any of the criteria for the study drug discontinuation and is removed from the study. See "15.1 Study drug discontinuation"). In addition, the combination of sargramostim with chemotherapy and radiotherapy is contraindicated. Except treatment/therapy mentioned above, there are no specific prohibited concomitant medications in this study. And steroids as standard treatment at each medical institution and approved antivirals, or others can be concomitantly used as part of standard treatment.

If a subject initiates use of invasive ventilator or ECMO, administration of the study drug will be terminated after use of these devices has been initiated (see "15.1 Study drug discontinuation"). The necessity to use these devices during the study period will be judged as part of the standard treatment against COVID-19 according to the disease condition and medical necessity of the subject.

The investigators will record and report the concomitant medications/therapies used during the study (see 13.14 Confirmation of concomitant medication/therapy).

12 Management of Subject

If a subject is discharged from the hospital during the study period, the subject shall be appropriately instructed to receive the observation/examination at the timing specified in the "2 Observation and Examination Schedule" and to avoid pregnancy or breastfeeding until the last observation for a female subject of childbearing potential.

13 Measurement of Parameters

In accordance with "2 Observation and Examination Schedule", observations/examinations and evaluations will be performed, and the date and the results of observations/examinations will be recorded in the source documents such as the medical record. In addition, the prespecified data will be entered in the eCRF.

After obtaining written informed consent from the candidate patient and the legally acceptable representative in accordance with "8.2 Timing and procedures for obtaining informed consent", the investigators will perform a screening test. The screening test results will be entered in the eCRF. The data at the screening test may be used if they have been collected within 7 days prior to informed consent. In addition, when the examinations scheduled on Day 0 have been collected prior to informed consent, the data may be used if they were collected within 2 days prior to Day 0.

Additional observations/examinations may be performed at the discretion of the investigators depending on the results of the scheduled observations/examinations, even if those additional observations/examinations are not included in the scheduled observations/examinations. If the scheduled observations/examinations were not performed, the reason should be clarified.

The study period will be from the day of informed consent to the day of the last observation (Day 28) (including the case of discharge from hospital). After completion of the final observations/examinations, completion of the study and the date of completion will be recorded in the eCRF.

Refer to "15 Criteria for Discontinuation of Study, Subject and Study Drug " for premature termination of study participation of a subject or discontinuation of study drug.

Follow-up examination will be conducted according to "14.8 Observation of AEs".

13.1 Subject characteristics

The date of informed consent, date of birth, sex, height, weight, alcohol consumption, smoking history, presence or absence of allergies (drugs, food, etc.), date of COVID-19 onset, date of collection of a sample where SARS-CoV-2 was detected positive by PCR test, past medical history/current medical condition, prior medication/therapy, concomitant medication/therapy.

The date and the results of the observations/examinations will be entered in the eCRF.

13.2 Physical examination

The investigators will conduct physical examination (medical interview, inspection, palpation, and auscultation, etc.) according to the standard procedures of the medical institution, and the results will be recorded. Also, the date and the results of the examinations will be entered in the eCRF.

13.3 7-point ordinal scale

The investigators will evaluate the category on a 7-point scale, referring to Table 13.3-1. The evaluation results will be recorded. Also, the date and the results of the evaluation will be entered in the eCRF.

Table 13.3-1 7-Point Ordinal Scale

Category	Ordinal scale
1	Have died
2	Use an invasive ventilator or ECMO
3	Use a noninvasive ventilator or high-flow oxygen supply device
4	Require oxygen supply
5	Do not require oxygen supply but require continuous therapy (related to COVID-19 or others).
6	Do not require both oxygen supply and continuous therapy
7	Have been discharged from hospital

13.4 Vital signs

Blood pressure (systolic, diastolic), pulse rate, body temperature and respiratory rate will be measured and recorded. The date and the results of the measurements will be entered in the eCRF.

Blood pressure and pulse rate will be measured after resting for about 5 minutes. The blood pressure may be measured in either supine or sitting position, but the posture for blood pressure measurement should remain constant throughout the study whenever possible.

The site (forehead, ear, axilla, etc.) for body temperature measurement in the same subject should remain constant throughout the study whenever possible.

13.5 12-lead Electrocardiography

Twelve-lead electrocardiography (ECG) will be performed after resting for at least 5 minutes in accordance with the standard procedure of the medical institution.

The investigators or the designated, will confirm and assess the electrocardiogram, and record. The date of assessment, heart rate, and assessment results will be entered in the eCRF.

13.6 Laboratory tests (blood chemistry, hematology, urinalysis, and pregnancy test)

The following items will be measured at the medical institution. If the measurement results deviate from the reference value, the investigators will assess whether the deviation is clinically significant. Pregnancy test will be performed only for women of childbearing potential. Pregnancy test will not necessarily be required for a female subject considered unable to become pregnant due to the following reasons: menopause (amenorrhea for at least 12 months without medical reasons), total hysterectomy, or that she does not get the first menstruation yet. The date of the sample collection and the test results will be entered in the eCRF.

Abnormal changes in laboratory test values that are judged by the investigators to be applicable to adverse events will be reported separately as adverse events (see "14.1 Definitions of AE").

Table 13.6-1 List of Laboratory Parameters

Hematology	Red blood cells count, white blood cells count, differential white leucocytes (neutrophils, lymphocytes, monocytes, eosinophils, basophils), platelets count, hemoglobin, hematocrit
Blood chemistry	Total protein, albumin, AST (GOT), ALT (GPT), γ -GTP, ALP, LDH, CK (CPK), total bilirubin, total cholesterol, HDL-cholesterol, LDL-cholesterol, triglycerides (TG), BUN, creatinine, blood glucose, Ca, Na, K, P, Cl
Urinalysis	Occult blood, protein, glucose, urobilinogen
Pregnancy test	Urine hCG or serum hCG

13.7 Percutaneous oxygen saturation (SpO₂)

Percutaneous oxygen saturation (SpO₂) will be measured using a pulse oximeter on breathing of room air in bed rest. The date and the test results will be entered in the eCRF

13.8 Inflammatory marker

C-reactive protein (CRP) will be measured at the medical institution. The date of sample collection and the test results will be entered in the eCRF.

13.9 Cytokines

The following cytokines will be measured at the central laboratory. Measurement results will not be disclosed until the code breaking after the clinical study has been completed. The date of sample collection will be entered in the eCRF : IL-6, IL-1 β , TNF- α , IL-10, CCL17, CXCL9, MMP-12.

Sample collection and storage will be performed in accordance with the procedures specified separately.

13.10 Arterial blood gas analysis (PaO₂, PaCO₂, A-aDO₂, others)

The subject will take a rest for at least 5 minutes under breathing of room air (when oxygen is being inhaled, the device will be temporarily removed) in a supine position on bed in a physicians room or in an examination room, then SpO₂ will be confirmed to be stable on a pulse oximeter and the blood sample will be collected from the artery using a blood collection kit designated by the medical institution. After blood sample is collected, the sample will be mixed adequately, and blood gas will be measured within 30 minutes using a blood gas analyzer. If it takes more than 10 minutes from blood collection to measurement, the blood sample will be kept in ice water. Whether the examination is possible or not will be determined to secure the subject safety considering the following criteria:

- (1) SpO₂ 94% or lower under the use of nasal high flow or mask
- (2) SpO₂ 93% or lower under oxygen supply of 4 L/min or more using nasal cannulas

A-aDO₂ will be automatically calculated using the following formula and automatically entered in the eCRF:

$$A-aDO_2 = (PB - PH_2O) \times FiO_2 - PaCO_2/R + \{PaCO_2 \times FiO_2 \times (1-R)/R\} - PaO_2$$

, where

PB: barometric pressure (measured at each medical institution)

PH₂O: partial pressure of water vapor in inspired air (47 mmHg)

R: respiratory quotient (0.80)

FiO₂: fraction of inspiratory oxygen (0.21)

The date of sample collection and the measurement values of PBs and PaO₂, PaCO₂, pH, SaO₂ will be entered in the eCRF

13.11 Chest HRCT or plain chest CT or chest X-ray

Chest high-resolution computed tomography (HRCT), plain chest CT, or chest X-ray will be performed in each subject (or at each medical institution) by choosing one of the above-mentioned examinations, and the same examination will be performed throughout the study period.

Details of image capturing condition and CT values for performing chest HRCT will be described in the HRCT testing procedures, whereas other image capturing procedures will be performed according to the standard procedures of the medical institution. Quantitative assessment of findings such as ground-glass opacity for the chest HRCT images will be performed using densitometry according to the procedures specified separately. The date of examination and the assessment results will be entered in the eCRF.

Image capturing of plain chest CT and chest X-ray will be performed according to the standard procedures of the medical institution, and those images will be assessed by the radiologist or the investigators of the medical institution. The assessment results will be recorded. The date of examination and the assessment results will be entered in the eCRF.

13.12 Oxygen requirement

The investigators will evaluate the category of oxygen requirement of a subject classified in 5 categories, referring to Table 13.12-1. The date of evaluation and the results will be entered in the eCRF.

Table 13.12-1 Oxygen Requirement

Category	Ordinal scale
1	Require oxygen supply of 4 L/min or more using oxygen mask
2	Require oxygen supply of 2 L/min or more using nasal cannulas
3	Require oxygen supply of less than 2 L/min using nasal cannulas
4	Do not require oxygen supply but feel shortness of breath during walking or moving
5	Do not require oxygen supply and do not feel shortness of breath during walking or moving.

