Considering the mechanism of action of sargramostim, patients with clinically diagnosed pneumonia whose respiratory function is suggestively decreased are to be included in the study. In addition, patient population without use of invasive ventilator yet (the category of a patient that falls into one of Category 3 to 5 on a 7-point ordinal scale (see Table 13.3-1)) is to be chosen in order that an accurate dose of study drug can be administered by inhalation.

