7.2 Exclusion criteria

Subjects who meet any of the following criteria will be excluded. Unless otherwise stated, the following criteria refer to those at the time of screening.

- (1) Patients who have allergic reactions or hypersensitivity to the active ingredient of the test drug (sargramostim) or its additives (mannitol, sucrose and tromethamine) or yeast-derived products or other.
- (2) Patients who have been participating in other intervention studies, such as a study on unapproved pharmacotherapy, within 90 days prior to screening.
- (3) Patients who have experienced off-label use of approved drugs (including those for COVID-19 treatment other than steroids and favipiravir as standard treatment) within 7 days prior to screening.
- (4) Patients who are not expected to survive longer than 24 hours after commencement of study drug administration
- (5) Patients who are using invasive ventilator or extracorporeal membrane oxygenation (ECMO).
- (6) Patients who have a chronic respiratory disease requiring continuous home oxygen therapy or ventilator use.
- (7) Patients with an underlying condition that is considered very unlikely to withdraw ventilator (e.g., motor neuron disease, Duchenne muscular dystrophy, rapidly progressive interstitial pulmonary fibrosis).
- (8) Patients who have a disease including bronchial asthma, lower respiratory tract infections, or interstitial lung diseases that may affect the assessment of the clinical study, since before the symptom onset of COVID-19.

- (9) Patients who have a disease including leukemia or leukocytosis that causes leukocytosis.
- (10) Patients who have a chronic kidney disease requiring dialysis.
- (11) Patients who have severe liver failure (Child Pugh grade C).
- (12) Patients who are pregnant or breastfeeding or who are positive on pregnancy test.
- (13) Patients aged 80 years or older who have/are cardiac disease, cerebrovascular disorder, obese patient (BMI 30 or higher), dyslipidemia, hypertension or diabetes
- (14) Other patients considered inappropriate by the investigators for inclusion in the study

[Rationale]

- In order to minimize the burden of the medical front for the treatment of COVID-19 patients, the assessment results at screening are to be applied as much as possible, as far as the results are considered reasonable.
 - (1) It was set to ensure the safety of subjects.

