2) For patients who were categorized in each category on a 7-point ordinal scale on Day 14 (or at the last observation the point) and Day 28 (or at the last observation time point between Day 15 and Day 27), the p-values (Wilcoxon's rank sum test) of the differences between groups will be calculated.

2.1.2.10.2.9 Distribution and proportion of patients in each category of oxygen requirement until Day14

(1) Analysis set : FAS

(2) Analysis item : oxygen requirement

(3) Time point : Day 0 to Day 14

(4) Analytical method :

1) The number of patients and the proportion in each category on the oxygen requirement shown in Table 2.2 until Day 14 will be summarize by treatment group and by time point (number of patients, %). In addition, a bar chart showing the percentage of each category will be prepared by treatment group and by time point.

2) For patients who were categorized in each category on the oxygen requirement on Day 5 and Day 14, the p-values (Wilcoxon's rank sum test) of the differences between groups will be calculated.

Table 2.2 Oxygen requirement

Category	Ordinal scale
1	Require oxygen supply of 4 L/min or more using oxygen mask
2	Require oxygen supply of 2 L/min or more using nasal cannulas
3	Require oxygen supply of less than 2 L/min using nasal cannulas
4	Do not require oxygen supply but feel shortness of breath during walking or moving
5	Do not require oxygen supply and do not feel shortness of breath during walking or moving

Table 2.3 Definition of event/censoring in Time to event analysis

Analysis item	Event/ Censoring	Definition of event/censoring	Period

 
Period to the first improvement by at least 2-rank between baseline and Day 28 on a 7-point ordinal scale 
 
Period from baseline to the day of discharge
 
Period from baseline to shifting to Category 6 or 7 on a 7-point ordinal scale
 
Period from baseline to shifting to Category 5 on a 7-point ordinal scale
 
Period to from baseline to improvement by 1 rank or more on a 7-point ordinal scale
 
 
 
	Event	A patient who developed an event	Period until the onset of the first event
	Censoring	A patient who completed the study without any event	Period until the last observation day
		A patient who discontinued or died	Censored after complementing 29 days*

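### The oxygen-requirement scale has no category for living patients on high-flow oxygen, a ventilator or ECMO, so the plan leaves their Day 5 and Day 14 ratings either blank and untested or pooled with mask oxygen

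*Protocol*

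**What the plan says.** **The scale.** Secondary endpoint (8) is the distribution of oxygen requirement to Day 14. Protocol 13.12 has the investigators place each subject in one of five categories. Three involve oxygen. The worst is "Require oxygen supply of 4 L/min or more using oxygen mask"; next comes "Require oxygen supply of 2 L/min or more using nasal cannulas"; and the mildest of the three is "Require oxygen supply of less than 2 L/min using nasal cannulas". The other two are without oxygen. Protocol 5.2.1.9 defers the detail of the categories to the SAP, but SAP Table 2.2 repeats the same five rows.

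**Who is rated.** The rationale in Protocol section 7, referring to the 7-point scale, describes a "patient population without use of invasive ventilator yet (the category of a patient that falls into one of Category 3 to 5". Category 3 of that scale (Table 13.3-1) is "Use a noninvasive ventilator or high-flow oxygen supply device". SAP 2.1.2.15 makes baseline category 3/4/5 a subgroup factor, so such patients are expected. Protocol 7.2 excludes "Patients who are using invasive ventilator or extracorporeal membrane oxygenation (ECMO") at entry. Under Protocol 15.1, a subject who later needs these devices stops study drug but stays in the scheduled study procedures if they can be performed and no withdrawal criterion is met.

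**The test.** SAP 2.1.2.10.2.9 sets out the between-group tests in these words: "For patients who were categorized in each category on the oxygen requirement on Day 5 and Day 14, the p-values (Wilcoxon's rank sum test". SAP 2.1.2.14(4) shows missing efficacy categories as their own category and counts them in the denominator of summaries. It gives them no rank.

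**The concern.** Protocol 5.2.1 justifies this endpoint as an indicator of respiratory failure, but the scale cannot record the most severe living states. High-flow or ventilator use on Day 5 or Day 14 is a post-randomisation outcome. If those patients are left blank, whether a patient enters the test depends on how that patient fared. A drug that keeps patients off such support then gets no credit in this test. If it moves them only as far as mask oxygen, the comparison can point the wrong way: those patients enter the active arm as Category 1, while their control counterparts are absent. If they are placed in Category 1 instead, two levels of severity are merged. If sites differ, one endpoint is rated under several conventions.

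**Working it through.** **1. Mapping states to rows** (Tables 13.3-1 and 13.12-1)

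| State of a living patient | 7-point category | Oxygen-requirement row |
|---|---|---|
| Invasive ventilator or ECMO | 2 | none |
| Noninvasive ventilator or high-flow device | 3 | none |
| Mask, 4 L/min or more | 4 | 1 |
| Mask, below 4 L/min | 4 | none |
| Nasal cannulas, 2 L/min or more | 4 | 2 |
| Nasal cannulas, below 2 L/min | 4 | 3 |

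The second row can occur from Day 0; the first only after randomisation.

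**2. Size under assumptions.** The plan gives no operating figure for this endpoint and no rate for the unlisted states; its 82.1% power belongs to the primary log-rank test. Inputs from the documents: 40 active and 20 control patients, two-sided 5%. Assumed: a share q_c of control and q_a of active patients is on high-flow, a ventilator or ECMO on the test day, and everyone else has the same distribution in both arms (15/25/25/20/15% over Categories 1 to 5).

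The probability that an active patient ranks better than a control patient, counting ties as half, is:
- separate worst rank: 0.5 + (q_c − q_a)/2;
- placed in Category 1: the same formula with each q replaced by q + 0.15(1 − q);
- dropped: 0.5, because the remaining distributions are identical by assumption.

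At 40%/10%: worst rank 0.5 + 0.30/2 = 0.65. In Category 1 the shares are 0.40 + 0.15 × 0.60 = 0.490 and 0.10 + 0.15 × 0.90 = 0.235, which gives 0.5 + 0.255/2 = 0.63.

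Simulated Wilcoxon rejection rates (repeat runs agree to within about two percentage points):

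| Control / active share | Expected patients affected | Worst rank | Category 1 | Dropped |
|---|---|---|---|---|
| 40% / 10% | 8 + 4 = 12 | 48% | 37% | 5% |
| 30% / 10% | 6 + 4 = 10 | 25% | 18% | 4% |
| 20% / 10% | 4 + 4 = 8 | 10% | 8% | 5% |

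With equal shares of 20% in both arms, rejection is about 5% whether the patients are ranked worst or dropped, so the added rank does not inflate type I error.

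**3. Direction, by hand.** Assume control has 30% on high-flow or a ventilator, 10% in Category 1 and 60% better; active has 10%, 30% and 60%, with the better patients spread identically.
- Worst rank: 0.30 × 0.30 + 0.60 × 0.40 + ½(0.10 × 0.30 + 0.30 × 0.10 + 0.60 × 0.60) = 0.09 + 0.24 + 0.21 = 0.54, in favour of active.
- Dropped: Category 1 holds 30/90 = 33% of active and 10/70 = 14% of control. The probability is (2/3)(1/7) + ½[(1/3)(1/7) + (2/3)(6/7)] = 0.095 + 0.310 = 0.40, against active.
- Placed in Category 1: 40% in each arm, a tie at 0.50.

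**The case against.** A reader might infer that these patients certainly drop out of the tests. The documents do not support that. Protocol 13.12 asks for one of five categories and offers no unratable option, so using the worst row is at least as natural as a blank. Under that reading most of the signal survives (37% against 48% in the first case) and the reversal becomes a tie. This stands, and it makes the loss conditional. But nothing instructs sites to use Category 1. High-flow nasal oxygen could even be read as Category 2, although Protocol 13.10 names nasal high flow separately from nasal cannulas.

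The assumed rates can also be challenged. The largest effect needs 40% of controls on such support and a fourfold difference between arms. The 5% result after dropping follows from assuming identical distributions elsewhere. Both points stand; at 20%/10% even the separate rank rejects in only 10% of trials.

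The SAP has a route for blanks: 2.1.2.14(3) sends missing data not otherwise specified to the Case Review Committee, and 2.1.2.14(4) keeps blanks visible by arm. The same wording about categorised patients introduces the 7-point Wilcoxon tests, so it may be stock phrasing rather than a deliberate exclusion. This softens the point, but no rule sets a rank.

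Finally, a reader might infer that the trial gives no credit for avoiding ventilation. It does, elsewhere: the 7-point scale includes these states and feeds the primary endpoint, the analyses of shift to Category 1 or 2, and the Day 14 and Day 28 Wilcoxon tests.

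**Conclusion.** The gap holds on the text alone: eligible patients, and patients who worsen but stay in follow-up, have no oxygen-requirement category, and the SAP does not close the gap. What follows depends on site practice that the plan leaves open. Blanks remove patients from both tests according to post-randomisation severity and can reverse the direction in the pattern shown above. Category 1 costs 48 − 37 = 11, 25 − 18 = 7 or 10 − 8 = 2 percentage points of power in the three cases. Mixed practice makes ratings inconsistent between sites. All these sizes rest on assumed rates; the reversal shows what can happen and is not a forecast. The point is limited to living patients and to one secondary endpoint. The primary endpoint and the other 7-point analyses are unaffected. It should be corrected, but it does not threaten the main conclusion.

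**What to change.** Add a rank worse than Category 1, for noninvasive or invasive ventilator, ECMO or high-flow device, to the synopsis table, Protocol Table 13.12-1 and SAP Table 2.2. Fill it by derivation: any living patient in 7-point Category 2 or 3 on a given day takes this rank that day, whatever the site entered. State in SAP 2.1.2.10.2.9 that the Day 5 and Day 14 Wilcoxon tests use it.

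Masks below 4 L/min also lack a row, and the sponsor should state where they are rated. Widening Category 1 to a mask at any flow is not proposed: it would rank a low-flow mask worse than nasal cannulas at 4 L/min or more, a state that Protocol 13.10 anticipates. Nor can the 7-point rating identify these patients, since all conventional oxygen falls in its Category 4.

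The cost is wording in three tables, one derivation rule and one sentence on the tests. No new data are needed, because both scales are rated daily, after the second inhalation, over this period. The analysed scale has six ranks instead of five, so the summaries and charts must be updated.
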